## 10.3 Pharmacology Study Design, Modeling, and Analysis

Oral and LA regimens with the proposed initial doses in this pediatric population are expected to achieve plasma concentrations within an acceptable range of those observed clinically in adolescents and adults. Initial doses selected for each weight band, based on prior data and modeling, are described in Section 5.

Pharmacokinetic blood samples will be collected as noted in Section 6 and Appendix I. Of note, PK samples need to be protected from light from sampling through analysis as detailed in the LPC.

Cohort 1 (with oral lead-in): Plasma concentrations for both CAB and RPV will be measured in at least the first 8 participants across Weight Bands 1 and 2, and at least the first 8 participants across Weight Bands 3, 4, and 5 according to the Rich Sampling Schedule as follows:

- Oral dosing
  - O Wk. 2: Pre-dose, 1, 2, 3, 4 and 8h post dose (6 samples)
- Long-acting injectable dosing:
  - o Wk. 4b: Pre-dose and 2h and 24h post dose,
  - o Wk. 5: Day 2-7 post-dose,
  - o Wk. 6: Day 12-16 post-dose,
  - o Wk. 8: pre-dose,
  - o Wk. 9: Day 3-7 post-dose,
  - Pre-dose prior to injections at Wk. 12, Wk. 16, Wk. 24, Wk. 32, Wk. 40, Wk. 48, Wk, 56, Wk. 64, Wk. 72.

Cohort 1 (with oral lead-in) and Cohort 2a (with oral lead-in): Once the proposed dosing regimens have been evaluated in each weight band and data are sufficient for the PK parameter estimates for both oral and IM dosing, then the Limited Sampling Schedule (below) will be used for the remainder of participants (through Week 72 for Cohort 1 and Week 48 only for Cohort 2a). Operational guidance for implementing the Limited Sampling Schedule for newly enrolling and currently enrolled participants will be provided in the IMPAACT 2036 MOP with additional communication provided to site teams at the time of implementation in a Memorandum of Operational Instruction.

- Oral dosing
  - o Wk. 2: Pre-dose and 3h post dose (2 samples)
- Long-acting injectable dosing:
  - o Wk. 4b: Pre-dose and 2h post dose
  - o Wk. 5: Day 2-7 post-dose,
  - o Pre-dose prior to injections at Wk. 8, Wk. 16, Wk. 24, Wk. 32, Wk. 40, Wk. 48, Wk56, Wk. 64, Wk. 72.

Cohort 2b (straight to IM dosing): For participants who do not receive oral doses, and start with IM dosing at Entry, the following IM-only Sampling Schedule will be used:

- Long-acting injectable dosing:
  - o Entry: Pre-dose and 2h and 24h post dose,
  - o Day 3: Day 2-7 post-dose,
  - Wk. 2: Day 12 16 post-dose,
  - o Pre-dose prior to injections at Wk. 4, Wk. 12, Wk. 20, Wk. 28, Wk. 36, Wk. 44.

All Cohorts (Cohorts 1, 2a and 2b)

- LSFU
  - o Single PK sample collected at LSFU Week 4, 8, 24, 36 and 48 visits.

Assay Site: Plasma pharmacokinetic samples collected will be sent to the IMPAACT Pharmacology Laboratory listed in the IMPAACT 2036 LPC for both CAB and RPV containing specimens. Sample collection, processing, storage and shipping details are provided in the IMPAACT 2036 LPC.

Methods to be used: All assay methods will be standardized with a filed Methods Report, under Good Laboratory Practice (GLP) conditions and cross-validated with primary assay providers used for CAB and RPV. The assays will be performed using high-performance liquid chromatography and tandem mass spectrometry (HPLC/MS/MS).

Reporting of Assay Data: PK samples from participants in Cohort 1 who are following the Rich Sampling Schedule will have assays performed in real-time through Week 24. Assaying of samples from the Wk. 32 through the Wk. 48 and Wk. 72 visits in the Rich Sampling Schedule, and all assays from the Limited Sampling Schedule (Cohorts 1 and 2a) may be performed in batches (refer to LPC for shipping schedule), and upon team request. PK samples from participants in Cohort 2b who are following the IM-only Sampling Schedule will have the assays performed in real-time up through Week 20. Samples from Wk. 28 through Wk. 44 may be assayed in batches and upon team request. PK samples collected from any Confirmation of Virologic Failure visit will be assayed as requested by the team.

#### 10.3.1 Interim Analyses

The first interim analysis will be performed once 8 dose-evaluable participants across Weight Bands 1, 2, and 3 have completed the Wk. 12 visit with at least two dose-evaluable participants in the lowest of these weight bands (20-24.9 kg). If the observed median Wk. 12 concentrations meet the acceptance criteria for CAB and RPV (below), then the lighter Weight Bands, 4 and 5 will open to enrollment. See "Potential Dose Modification" section below for additional details.

A second interim analysis is planned to take place once Weight Bands 4 and 5 are open to accrual and 8 dose-evaluable participants across Weight Bands 3, 4, and 5 have completed the Wk. 12 visit with at least two dose-evaluable participants in the lowest weight band (10-13.9 kg). If the observed median Wk. 12 concentrations meet the acceptance criteria for CAB and RPV (below), then Cohort 2 can enroll across all weight bands. See "Potential Dose Modification" section below for additional details.

Additional evaluations of CAB and RPV pharmacokinetics may be performed for specific weight bands, for either Cohort 1 or Cohort 2, depending on the ongoing study findings, safety data, and/or any proposed changes to the initial weight-band dosing regimens (changes in dose amounts and/or dose intervals).

#### PK Acceptance Criteria

#### Oral CAB

The CAB PK acceptable criteria following oral administration is:

- A median Wk. 2 AUC0-τ between 38 and 277 and mcg\*h/mL (the lower bound of the 95% CI for AUC following 10mg once daily to the upper bound of the 95% CI for AUC following 60mg once daily in adults living with HIV in LAI116482 (LATTE))
- Median trough (at the end of the oral dosing interval; Cτ) concentrations ≥0.45 mcg/mL (5th percentile of the observed CAB trough concentration following the initiation injection in Phase 3 studies in adults)
- Median  $C_{max} \le 22.5$  mcg/mL that was observed in the TQT study in adults without any impact on QT interval.

### Oral RPV

The RPV PK acceptable criteria following oral administration is:

- A median Wk. 2 AUC0- $\tau$  between 1250 and 4166 ng\*h/mL (approximately 60-200% of the geometric mean in adults, which is 2083 ng\*h/mL).
- Median trough  $(C_{\tau})$  concentrations  $\geq 17.3$  ng/mL (5th percentile of the observed RPV trough concentration following the initiation injection in Phase 3 studies in adults)
- Median  $C_{max} \le 450$  ng/mL (determined as not posing an increased risk for QT interval prolongation based on PK/PD modeling and simulation for adult TQT studies)

For this study, AUC of a selected RPV dose under fed and steady-state conditions will be the primary PK parameter for determination of the acceptability of the RPV oral dose, but the  $C_{max}$  and  $C_0$  of RPV will also be taken into consideration.

#### CAB LA

The CAB PK acceptable criteria following LA administration is:

• A median Wk. 12 (Cohort 1) or Wk. 8 (Cohort 2b) trough (prior to next LA dose; Ct) concentration between 0.71-6.7 mcg/mL

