#### 6.1.2 Additional Considerations for a Q8W Injection Schedule

In the event of a dosing regimen modification (see Section 5.1.2), the follow-up visit schedule for each cohort will remain per Sections 6.3 through 6.6 and per Appendix I. However, injections and other select visit procedures, as specified below, will only occur at a Q8W frequency.

Participants newly enrolling into the study on a Q8W injection schedule will have injectable study product administered at the following visits:

- For Cohort 1 (through Week 72) and Cohort 2a (through Week 48 only): Weeks 4b, 8, 16, 24, 32, 40, 48, 56, 64, and 72.
- For Cohort 2b: Entry, Week 4, and at Weeks 12, 20, 28, 36, 44.

When receiving injectable study products on a Q8W schedule, acceptability/tolerability assessments for participants and parents/caregivers and all laboratory evaluations (including urine pregnancy tests and all bloodwork) will be administered on a Q8W schedule and will only take place at injection visits. Non-injection visits for participants on a Q8W injection schedule may be conducted in person or telephonically.

See the IMPAACT 2036 MOP for further details regarding implementation of a dosing regimen modification and associated procedural changes when moving from Q4W to Q8W dosing.

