## 6.4.5 Week 8, 12, and 16 Visits: Cohort 2b

Cohort 2b V	Neek 8, 12,	and 16 Visit Procedures
Behavioral a	ınd	Provide adherence counseling
Counseling		Provide contraceptive counseling^
_		Administer participant acceptability/tolerability assessment based upon participant age, as specified in the IMPAACT 2036 MOP
Clinical		Update medical and medications history
		Perform targeted physical exam
		Identify/review/update adverse events
Laboratory	Blood	Collect blood for:
		Hematology: CBC (WBC, RBC, hemoglobin, hematocrit, MCV, MCHC) with differential, ANC (absolute neutrophil count), and platelet count
		Chemistries: Creatinine, eGFR, CK, Direct bilirubin, Total bilirubin, BUN, AST, ALT, Lipase, Albumin
		• HIV-1 RNA
		PK evaluation (Week 12 only): Single pre-dose sample
	Blood or Urine	Pregnancy test^
Study produ	ct	Prescribe, prepare, and administer injectable study products

^ For participants of childbearing potential.

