## 10.2.1 Cohort 1 Primary PK Outcome Measures (CAB and RPV)

- PO dosing: Wk. 2 AUC, CL/F, Cmax, Tmax, and pre-dose concentrations (C0)
- LA dosing (starting at Week 4b): Wk. 5 concentrations (C5WK), Wk. 12 concentrations (C12WK), trough concentrations (Ct) prior to IM doses through Wk. 24 and accumulation ratio (Wk. 24:Wk. 8).

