#### RPV LA

The RPV PK acceptable criteria following LA administration is:

• A median Wk. 12 (Cohort 1) or Wk. 8 (Cohort 2b) Ct between 25-100 ng/mL

The study team will review all of the PK parameters following oral and long-acting CAB and RPV, safety and tolerability/acceptability data to determine if dose modifications are warranted (for each drug, for each formulation and for each weight band).

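### The Cohort 2b PK acceptance criteria use a Week 8 trough that is never sampled, and for children starting on Q8W Section 6.1.2 conflicts with Section 10.3 and Appendices I and II over blood at Weeks 5, 12 and 20

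*Protocol*

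**What the plan says.** **Criteria.** Section 10.3.1 sets the CAB LA criterion at "A median Wk. 12 (Cohort 1) or Wk. 8 (Cohort 2b) trough (prior to next LA dose", with bounds of 0.71-6.7 mcg/mL. The RPV LA criterion uses the same weeks, "A median Wk. 12 (Cohort 1) or Wk. 8 (Cohort 2b", with bounds of 25-100 ng/mL. Both Cohort 1 interim analyses use the observed median Week 12 concentrations.

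**Cohort 2b sampling.** After Entry, Day 3 and Week 2, Section 10.3 lists "Pre-dose prior to injections at Wk. 4, Wk. 12, Wk. 20, Wk. 28, Wk. 36, Wk. 44". The visit table in Section 6.4.5, which covers Weeks 8, 12 and 16, agrees: "PK evaluation (Week 12 only): Single pre-dose sample".

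**Primary PK outcomes, Cohort 1.** Section 10.2.1 names "Wk. 5 concentrations (C 5WK ), Wk. 12 concentrations (C 12WK", together with troughs through Week 24.

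**Q8W rule.** Section 6.1.2 says that laboratory evaluations ("including urine pregnancy tests and all bloodwork) will be administered on a Q8W schedule and will only take place at injection visits"). It lists the Cohort 1 injection visits as Weeks 4b, 8, 16, 24 and every eight weeks after that, and it lets other visits be done by telephone.

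**Appendix I-A.** Footnote 6, which allows omission at Q8W non-injection visits, marks the laboratory rows only for Weeks 28-72. The laboratory cells at Week 5 and at Weeks 8-20 do not carry it.

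**The concern.** A decision rule needs a sample at the time that it names. Cohort 2b children without an oral lead-in have only the LA criteria, and Section 10.3.1 allows further PK evaluations in Cohort 2 that can lead to a dose change. A criterion at an unsampled week leaves the team to substitute another week after seeing the data.

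The second problem arises only if injections move to Q8W. Under Section 5.1.2, children still in oral lead-in at a switch receive Q8W injections, and Section 10.3.1 lets new children start on Q8W. For them Section 6.1.2 and the appendices give sites different instructions about the same blood draws. At stake are two primary PK outcomes, the observed Week 12 values for the second interim analysis, and how often laboratory Grade 3 or higher events are looked for within a primary Week 24 proportion that pools both schedules.

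**Working it through.** No sample size or power figure is involved. The check sets required weeks against sampled weeks, and aligns the cohorts by days from first injection (Appendix II: from Week 4b in Cohort 1, from Entry in Cohort 2b).

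**Step 1. Alignment**

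| Days from first injection | Cohort 1 | Cohort 2b | Injection on Q4W | Injection on Q8W |
|---|---|---|---|---|
| 28 | Week 8 | Week 4 | yes | yes |
| 56 | Week 12 | Week 8 | yes | no |
| 84 | Week 16 | Week 12 | yes | yes |
| 140 | Week 24 | Week 20 | yes | yes |

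The two criterion weeks are thus the same point, day 56.

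**Step 2. Cohort 2b**
- PK sampled at Entry, Day 3 and Weeks 2, 4, 12, 20, 28, 36, 44. Required: Week 8. It is absent.
- Blood volumes in Appendix I-B agree: Weeks 8, 12 and 16 need 1 + 2 + 3 = 6 mL without PK and 6.5 mL with it, and the table shows 6-6.5 mL, so PK is taken at only some of these visits.
- On Q8W the second injection is at day 28 and the third at day 84. Day 56 lies 28 days into a 56-day interval, so a sample there would not be a trough.

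**Step 3. Cohort 1, starting on Q8W**
- Required for primary outcomes: Weeks 5 and 12. Injection visits to Week 24: 4b, 8, 16, 24. Both required weeks fall outside.
- Section 10.3 keeps a Week 5 PK sample on both the Rich and Limited Schedules, and the Q8W table in Appendix II keeps the Week 5 visit.
- Appendix I-A gives Week 5 as 1 + 2 + 0.5 = 3.5 mL and Weeks 8-20 as 6-6.5 mL. The minimum there is 6, not 0; for Weeks 28-72 the range is 0-7.5 mL. Appendix I-A therefore assumes blood at Weeks 12 and 20 whatever the schedule.

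**Step 4. Safety laboratory visits after the first injection, to Week 24**

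| Reading | Visits | Count |
|---|---|---|
| Q4W (Sections 6.3.5, 6.3.7, 6.3.8) | 5, 8, 12, 16, 20, 24 | 6 |
| Q8W, Section 6.1.2 literally | 8, 16, 24 | 3 |
| Q8W, Week 5 kept | 5, 8, 16, 24 | 4 |
| Q8W, Appendix I-A | 5, 8, 12, 16, 20, 24 | 6 |

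**Step 5. Limited Schedule**
- Sections 6.3.7 and 10.3 take Week 12 PK on the Rich Schedule only. On the Limited Schedule the Week 12 concentration is missing even on Q4W. The stated Rich Schedule minimum is 8 + 8 = 16 children, against at least 50 evaluable in Cohort 1.

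**Step 6. A time that every schedule samples**
- Day 84 (Cohort 1 Week 16, Cohort 2b Week 12) is a pre-dose sample on the Rich, Limited and injection-only schedules, and on Q8W it is the first end-of-interval trough.

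**The case against.** The strongest reply is that nothing which gates the study is broken. Initial dosing is Q4W in every weight band, and the Rich Schedule includes Week 12, so the first interim analysis can be evaluated. The second is touched only if contributing children start on Q8W; Band 3 children from the first analysis still count, and children past Week 12 at a switch stay on Q4W to Week 24. No stated gate rests on Cohort 2b: its PK is secondary, and its listed outcomes (troughs through Weeks 20 and 44, ratios to Week 4) have scheduled samples. For a move to Q8W, Section 10.3.1 applies the criteria to model-predicted concentrations. Section 6.1.2 also says that the visit schedule otherwise follows Sections 6.3 through 6.6 and Appendix I.

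Most of this stands, and it limits the point. A reader might infer that the PK rules as a whole cannot be evaluated. The documents do not support that, for the reasons just given, and Week 5 is an outcome, not part of any acceptance rule. Nor is it established that laboratory surveillance is halved or that the Week 5 concentration is lost in every Q8W child: both hold only if Section 6.1.2 overrides Section 10.3 and the appendices.

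Two things survive. Model predictions describe a regimen that the child is not receiving, so they supply neither an observed Cohort 2b Week 8 trough nor the observed median that the interim rule asks for. And Section 6.1.2 introduces its bloodwork sentence as an exception to the visit schedule, so pointing back to Appendix I does not settle which text governs.

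**Conclusion.** The point holds in two parts.

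1. **Unconditional.** The Cohort 2b acceptance criteria for CAB LA and RPV LA name a time with no scheduled PK sample. They cannot be evaluated on observed data on either schedule, and on Q8W the named time is not a trough.
2. **Conditional on children starting injections on Q8W.** Section 6.1.2 contradicts Section 10.3 and Appendix II on Week 5, and Appendix I-A on Weeks 5, 12 and 20. If Section 6.1.2 governs, these children have no Week 5 or Week 12 concentration, they add no observed Week 12 value to the second interim analysis, and they have 3 post-injection safety laboratory visits to Week 24 instead of 6. Across the possible readings the count runs from 3 to 6.

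In addition, the Week 12 concentration is a primary outcome that the Limited Schedule never collects, even on Q4W. The first interim analysis and Q4W children on the Rich Schedule are unaffected. How many children would start on Q8W cannot be known from the protocol.

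**What to change.** **(a) Tie each LA criterion to a scheduled sample.** On Q4W, add a 0.5 mL PK aliquot to the blood already drawn at Cohort 2b Week 8; this is day 56 and matches Cohort 1 Week 12. On Q8W, tie the observed-trough criterion to the day-84 pre-dose sample already scheduled (Cohort 1 Week 16, Cohort 2b Week 12). The team must confirm that the present bounds apply at that time. Moving the Q4W criterion to Cohort 2b Week 12 is not equivalent, since it would apply the same bounds after three injections instead of two.

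**(b) Reconcile Section 6.1.2 with Section 10.3 and Appendices I and II.** Limit its bloodwork restriction to visits after Week 24 (Cohort 2b: after Week 20), so that safety blood at Weeks 5, 12 and 20 and the Week 5 PK sample stay. Leave its rule on acceptability assessments alone: Appendix I already marks those for omission at earlier Q8W non-injection visits.

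**(c) State that the Week 12 concentration is reported for Q4W Rich Schedule children only.** Keeping Week 12 blood on Q8W would not help here, because that sample is mid-interval.

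**Cost.** Protocol wording, one 0.5 mL aliquot, and in-person visits for Q8W children at Weeks 12 and 20 (Cohort 2b: Weeks 8 and 16), which Appendix I already implies. For Q8W children in the second interim analysis, the observed trough arrives 84 - 56 = 28 days later than a Week 12 value would.

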# 6.3.7 Week 8, 12, 16, and 20 Visits: Step 2 - injection phase for Cohort 1 and Cohort 2a (Step 2 - injection phase)

^ For participants of childbearing potential.

Week 8, 12,	16, and 20	Visit Procedures (Step 2 – injection phase)
Behavioral and		Provide adherence counseling
Counseling		Provide contraceptive counseling^
		Administer participant acceptability/tolerability assessment based upon participant age, as specified in the IMPAACT 2036 MOP
		• Administer parent/caregiver acceptability/tolerability assessment (Week 8 only)
Clinical		Update medical and medications history
		Perform targeted physical exam
		Identify/review/update adverse events
Laboratory	Blood	Collect blood for:
		Hematology: CBC (WBC, RBC, hemoglobin, hematocrit, MCV, MCHC) with differential, ANC (absolute neutrophil count), and platelet count
		• Chemistries: Creatinine, eGFR, CK, Direct bilirubin, Total bilirubin, BUN, AST, ALT, Lipase, Albumin
		• HIV-1 RNA
		• PK evaluation: Single pre-dose sample at Week 8 and 16 for all participants and at Week 12 for participants on rich sampling schedule
	Blood or Urine	Pregnancy test^
Study produ	ct	Prescribe, prepare, and administer injectable study products

^ For participants of childbearing potential.

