### 6.16.2 Specimen Preparation, Testing, Storage, and Shipping

All specimens collected for this study will be labeled, transported, processed, tested, stored and/or shipped in accordance with the DAIDS policy referenced in Section 6.16 above, site and local laboratory SOPs, and the LPC. The frequency of specimen collection and testing will be directed by the Schedules of Evaluations in Appendix I and specifications for clinical management provided in Section 8. The Laboratory Data Management System (LDMS) will be used to document specimen collection, testing, storage, and shipping as specified in the LPC. Any specimens stored at the Screening Visit for participants who do not subsequently enroll in the study will be destroyed.

All HIV-1 RNA assays must be performed in a CLIA-certified (US) or VQA-certified (non-US) laboratory. CD4+ cell counts must be performed in a CLIA-Certified (US) or IQA-certified (non-US) laboratory.

HIV-1 genotypic and phenotypic resistance samples collected at the Confirmation of Virologic Failure visit must be processed and retained at the site laboratory, as specified in the LPC, pending HIV-1 RNA test results to confirm virologic failure. If virologic failure is confirmed, plasma from the Confirmation of Virologic Failure visit will be shipped to the designated testing laboratory (residual aliquots will be stored at the site laboratory) and resistance testing will be performed in real time. If virologic failure is not confirmed, all aliquots will remain stored at the site laboratory. Testing of resistance samples collected at the Entry and/or other visits will be directed by the CMC.

Specimens collected, processed, and stored at site laboratories for PK evaluations are generally expected to be shipped to the designated testing laboratory as follows, with more frequent shipping as requested by the protocol team:

- For Cohort 1 participants with the Rich Sampling Schedule, all available PK samples should be shipped upon completion of the following visits: Weeks 2, 12, 24, 48, and 72.
- For Cohort 1 participants with the Limited Sampling Schedule and Cohort 2a participants, all available PK samples should be shipped upon completion of the following visits: Weeks 24, 48, and 72 (Cohort 1 only).
- For Cohort 2b participants: all available PK samples should be shipped upon completion of the following visits: Week 4, 20, and 44.

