#### Potential Dose Modification

Dose adjustments for management of individual participant PK target exposures will not occur. In the event of failure with respect to safety and/or PK criteria that are deemed potentially avoidable by lower (or higher) exposure to the study drugs, as judged by the CMC, a dose adjustment will be considered for the applicable weight band. As noted in Section 5.1.2, dosing regimen modifications for each weight band may occur as needed following the Cohort 1 interim analyses and/or based on ongoing reviews of safety, PK, and all other relevant data, and will be implemented across all participants within the applicable weight band group. During the reviews of the data and based on the findings, the protocol team may decide whether to continue with Q4W dosing, move to Q8W dosing, change to a different dose on either the Q4W or Q8W schedule, or gather additional data on the initial Q4W dosing regimen for each weight band.

At the two planned interim analyses, and at any other additional relevant PK analysis, the PK parameters calculated from each individual participant will be used to predict that participant's exposure at Wk. 12 (Cohort 1) or Wk. 8 (Cohort 2b) if they were taking Q8W injections instead of Q4W (via modeling and simulation). Using the *predicted* Q8W dose interval trough concentrations from each participant, the same trough acceptance criteria will be applied as already noted in the protocol above. The same strategy will be used, if needed, during ongoing study PK analyses to assess alternate doses or dose intervals if particular weight-bands do not meet acceptance criteria for either the oral or the LA dosing. In other words, based on the observed PK data from each participant, those participants' predicted exposures on the new dose or dose regimen will be calculated, and the acceptance criteria will be applied to those individual participants' predictions on that new dose or dose interval.

When assessing whether to change the dose interval, if the median of the predicted concentrations from every 8 week dosing meets the LA dosing trough acceptance criteria, new participants in the corresponding Weight Bands may be initiated on every 8 week dosing. Ongoing study participants that enrolled on every 4 week dosing may also transition to every 8 week dosing after their week 24 visit.

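### The Cohort 2b acceptance criterion for injectable CAB and RPV is set at Week 8, a visit at which the Cohort 2b schedule draws no PK sample

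*Protocol*

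**What the plan says.** Section 10.3.1 gives the PK acceptance criteria for injectable dosing. For CAB LA the criterion is "A median Wk. 12 (Cohort 1) or Wk. 8 (Cohort 2b) trough", taken before the next injection, within 0.71-6.7 mcg/mL. For RPV LA it is "A median Wk. 12 (Cohort 1) or Wk. 8 (Cohort 2b", within 25-100 ng/mL. The Potential Dose Modification text names the same weeks when it describes predicting each child's "exposure at Wk. 12 (Cohort 1) or Wk. 8 (Cohort 2b" on Q8W injections.

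The Cohort 2b sampling list in Section 10.3 reads "Pre-dose prior to injections at Wk. 4, Wk. 12, Wk. 20, Wk. 28, Wk. 36, Wk. 44". Before those come Entry (pre-dose, 2 h and 24 h), Day 3 and Week 2. The visit table in Section 6.4.5, which covers Weeks 8, 12 and 16, has "PK evaluation (Week 12 only): Single pre-dose sample".

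Section 6.1.2 puts Cohort 2b injections on Q8W at Entry and Weeks 4, 12, 20, 28, 36 and 44. It restricts all laboratory work on Q8W to injection visits and lets the other visits be done by telephone.

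In Cohort 1, Section 6.3.7 takes a PK sample "at Week 12 for participants on rich sampling schedule", while the Limited Schedule in Section 10.3 is "Pre-dose prior to injections at Wk. 8, Wk. 16, Wk. 24, Wk. 32" and onward. Section 10.2.1 and Table 11 list the Week 12 concentration (C12WK) as a Cohort 1 primary PK variable without restricting it to the Rich Schedule.

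**The concern.** A decision criterion needs an observation to apply it to. Cohort 2b is the only group that starts injections without an oral lead-in. Section 9.5.1 asks for PK review in both cohorts, and Section 10.3.1 allows further PK evaluations in Cohort 2. If the criterion sits at a visit with no sample, whoever reviews the Cohort 2b data must either pick another visit or substitute a model prediction. The protocol does not say which, nor whether the same range then applies.

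A smaller point of the same kind concerns C12WK. It is presented as a primary outcome of Cohort 1, but only part of Cohort 1 is sampled at that visit.

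**Working it through.** No power or error-rate formula applies. The check compares the criterion weeks with the sampling and injection weeks, and then tests the reading against the blood volumes.

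**1. The protocol's own volume figure.** Appendix I-B gives 6-6.5 mL for the Cohort 2b column covering Weeks 8, 12 and 16. Hematology 1 mL + chemistries 2 mL + HIV-1 RNA 3 mL = 6.0 mL; with PK 0.5 mL the total is 6.5 mL. The stated range is reproduced, and it fits some visits in that column having no PK draw. Section 6.4.5 identifies Week 12 as the only one that has it.

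**2. Where Week 8 comes from.** In Appendix II, Cohort 1 Week 12 is 56 days after the first injection (Week 4b), and Cohort 2b Week 8 is 56 days after the first injection (Entry). On Q4W both follow two injections. The criterion was therefore shifted by four weeks to match. The Cohort 2b samples at Weeks 4, 12 and 20 match Cohort 1 Weeks 8, 16 and 24, which is the Limited pattern; the counterpart of the Rich Week 12 sample is missing.

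**3. The visits side by side.**

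| Visit | Earlier injections | Weeks since last injection | Injection due that day | PK sample scheduled |
|---|---|---|---|---|
| Cohort 1 Week 12, Q4W | 2 (4b, 8) | 4 | yes | Rich Schedule only |
| Cohort 2b Week 8, Q4W | 2 (Entry, 4) | 4 | yes | no |
| Cohort 2b Week 12, Q4W | 3 (Entry, 4, 8) | 4 | yes | yes |
| Cohort 2b Week 8, Q8W | 2 (Entry, 4) | 4 | no | no |
| Cohort 2b Week 12, Q8W | 2 (Entry, 4) | 8 | yes | yes |

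On Q4W the criterion visit is a true trough but has no sample. On Q8W it falls halfway between the Week 4 and Week 12 injections, so it is not a trough and no blood is drawn. The nearest later sampled visit, Week 12, differs from the Cohort 1 criterion visit in the number of injections (Q4W: 3 against 2) or in the interval (Q8W: 8 weeks against 4).

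**4. How many children.** Cohort 2 may enroll up to 40, with a minimum of 4 in each of 2a and 2b. Cohort 2b therefore has between 4 and 40 - 4 = 36 children. Scheduled observed Week 8 values: 0 for any number in that range.

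**5. C12WK in Cohort 1.** Section 3.1 guarantees Rich sampling for at least the first 8 children in Weight Bands 1-2 and the first 8 in Weight Bands 3-5: 8 + 8 = 16, against a target of at least 50 evaluable. Sixteen is a floor.

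**The case against.** The strongest reply is that nothing formal depends on the Cohort 2b value. The gates are the two Cohort 1 interim analyses, which use observed Week 12 medians. Cohort 2 opens only once both are available and acceptable. Cohort 2b PK is a secondary objective, and its declared outcomes in Section 10.2.3 (troughs through Weeks 20 and 44, and the ratios Week 20:Week 4 and Week 44:Week 4) are all at sampled visits. Potential Dose Modification applies the criteria to predicted exposures, and samples at Entry, Day 3, Week 2, Week 4 and Week 12 bracket Week 8. All of this stands, and it limits the consequence. It does not remove the contradiction: the acceptance criteria state the Cohort 2b median as a trough before the next dose, and no text says that a prediction replaces it for the regimen a child is actually receiving. The extra PK samples in Section 6.1.3 are for rare circumstances.

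A reader might infer more than the documents support:

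- **That the Cohort 1 gates also fail.** They do not; Rich Schedule children have the Week 12 sample.
- **That the Limited Schedule is an error.** The move to it is deliberate and is made only once the regimens have been evaluated and the PK data suffice. For the same reason, the documents do not show that a modified dose would go mainly to children who cannot be checked; Section 10.3.1 also tests predicted exposures on a new regimen.
- **That Cohort 2a misses its criterion.** No acceptance week is stated for Cohort 2a on injectable dosing, so there is no criterion for it to miss.
- **That shipping defeats real-time assay.** Section 6.16.2 says of Cohort 2b that "all available PK samples should be shipped upon completion of the following visits: Week 4, 20, and 44", but it introduces the list as a general expectation and allows more frequent shipping on request.

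**Conclusion.** The protocol contradicts itself on one decision criterion. The Cohort 2b acceptance trough for both injectable drugs is at Week 8, and no Cohort 2b child has a scheduled observed Week 8 concentration on Q4W or Q8W. An analysis plan cannot repair this alone, because both the criterion week and the sampling weeks are fixed in the protocol. Week 12 cannot stand in without comment, since it differs in injection count on Q4W and in interval on Q8W.

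The reach is limited to a criterion for a secondary, descriptive cohort of 4 to 36 children. Both Cohort 1 interim decisions remain workable, assuming the children who inform them are on the initial Q4W regimen of Table 2 and the Rich Schedule. Separately, C12WK is a Rich Schedule outcome in all but name, with at least 16 children. That is no shortfall for interim analyses of at least 8 each, but the primary outcome list should say so.

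**What to change.** Reconcile Section 10.3.1 (CAB LA, RPV LA and Potential Dose Modification) with Sections 6.4.5, 6.1.2 and 10.3 before Cohort 2 opens, in one of two ways.

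- **Move the criterion.** State the Cohort 2b criterion at a pre-dose visit already sampled, such as Week 12, and justify the range for the injection count and interval (three injections on Q4W, two on Q8W). This serves both schedules and costs wording only. Section 1.2.4 shows the same numerical ranges used as median targets at Week 16 in the adolescent study, so the sponsor has a starting point for that justification.
- **Add a sample, for Q4W children only.** Add a 0.5 mL pre-dose PK sample at Week 8 in Sections 6.4.5 and 10.3 and Appendix I-B. The visit total goes from 6.0 to 6.5 mL, within the range Appendix I-B already shows, plus one more sample to assay per child. This does not work on Q8W, where that visit has no injection or bloodwork, so a Q8W criterion visit would still have to be named.

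In Section 10.2.1 and Table 11, either label C12WK as a Rich Schedule outcome (at least 16 children) or replace it with a pre-dose concentration sampled on both schedules, such as Week 8 or Week 16. This also costs wording only.
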